4.6. Benefit:Risk Assessment

Summaries of findings from both clinical and non-clinical studies conducted with GSK2586881 can be found in the Investigator's Brochure (GlaxoSmithKline Document Number [2010N108777_00](#), 2015). The following section outlines the risk assessment and mitigation strategy for this protocol:

4.6.1. Risk Assessment

Potential Risk of Clinical Significance	Summary of Data/Rationale for Risk	Mitigation Strategy
Investigational Product (IP) [GSK2586881]		
Cardiovascular risk	During preclinical testing a brief period of non-sustained ventricular tachycardia was observed in one monkey receiving a dose of 20.8 mg/kg/day.	The dose used in this study is much lower and well below the No observed adverse effect level (NOAEL) for the 14 day repeat dose cynomolgus monkeys of 8 mg/kg/day.
Potential Reproductive/embryofetal risks	Preclinical studies have not been performed	Women of childbearing potential will be excluded from the study.
Potential for Immunogenicity	There has been no induction of an immune response to rhACE2 in either of the clinical studies to date in healthy subjects or participants with ARDS.	Patients will have routine monitoring of any immunological response that may occur. If an immunological response is seen the patient will be asked to return for further monitoring and assessment(s).
Potential for rash	In study ACE114622, rash was reported more frequently in subjects receiving GSK2586881, although only one event was considered drug-related.	Patients will be monitored for rash in the clinical trials.

Potential Risk of Clinical Significance	Summary of Data/Rationale for Risk	Mitigation Strategy
Study Procedures		
Effects of hypoxia (light headiness, headaches, nausea)	The subjects will be exposed to hypoxic conditions for approximately 90 minutes with a simulated altitude of 4000m	The subjects will be continuously observed and monitored with telemetry and pulse oximetry. Stopping criteria are included in the protocol.

4.6.2. Benefit Assessment

There will be no intended therapeutic clinical benefit to the subjects taking part in the study as it is a healthy volunteer study. However, subjects will undergo a medical evaluation during screening including physical exams, ECGs and laboratory assessments which may provide important health information.

By taking part in this study the subject will be contributing to the development of GSK2586881 for the treatment of pulmonary hypertension and ARDS.

4.6.3. Overall Benefit:Risk Conclusion

The design of the study is considered low risk to the subjects and justified based on the work carried out by other researchers, the safety information from the nonclinical studies and the two previous clinical trials carried out on GSK2586881.

5. SELECTION OF STUDY POPULATION AND WITHDRAWAL CRITERIA

Specific information regarding warnings, precautions, contraindications, adverse events, and other pertinent information on the GSK investigational product or other study treatment that may impact subject eligibility is provided in the IB.

Deviations from inclusion and exclusion criteria are not allowed because they can potentially jeopardize the scientific integrity of the study, regulatory acceptability or subject safety. Therefore, adherence to the criteria as specified in the protocol is essential.

5.1. Inclusion Criteria

A subject will be eligible for inclusion in this study only if all of the following criteria apply:

AGE
1. Between 18 and 40 years of age inclusive, at the time of signing the informed consent.

TYPE OF SUBJECT
2. Healthy as determined by the investigator or medically qualified designee based on a medical evaluation including medical history, physical examination, laboratory tests and cardiac monitoring. A subject with a clinical abnormality or laboratory parameter(s) which is/are not specifically listed in the inclusion or exclusion criteria, outside the reference range for the population being studied may be included only if the investigator [in consultation with the Medical Monitor if required] agree and document that the finding is unlikely to introduce additional risk factors and will not interfere with the study procedures. Note: Screened subjects with laboratory values outside of the normal range may be

repeated once for inclusion into the study at the discretion of the Investigator.

3. Screening echocardiogram of good quality, without clinically significant abnormalities, and with mild-moderate tricuspid regurgitation sufficient for the reliable estimation of PASP, as determined by the echocardiography core laboratory or responsible cardiologist.

Screening PASP within the normal range according to site standards.

4. Subjects have not resided at an altitude >1500m for more than 7 days in the last 4 month
5. Able to complete all study procedures.
6. Any contraindication (orthopaedic, cardiac etc.) to perform exercise on a bicycle ergometer.

WEIGHT

7. Body weight 50-100 kg (inclusive).

SEX

8. Male or female (non CBP)

Male subjects with female partners of child bearing potential must comply with the following contraception requirements from the time of first dose of study medication until at least five half-lives of study medication OR for a cycle of spermatogenesis following five terminal half-lives after the last dose of study medication.

- a. Vasectomy with documentation of azoospermia.
- b. Male condom plus partner use of one of the contraceptive options below:
 - Contraceptive subdermal implant
 - Intrauterine device or intrauterine system
 - Oral Contraceptive, either combined or progestogen alone [Hatcher, 2007a]
Injectable progestogen [Hatcher, 2007a]
 - Contraceptive vaginal ring [Hatcher, 2007a]
 - Percutaneous contraceptive patches [Hatcher, 2007a]

This is an all-inclusive list of those methods that meet the following GSK definition of highly effective: having a failure rate of less than 1% per year when used consistently and correctly and, when applicable, in accordance with the product label. For non-product methods (e.g., male sterility), the investigator determines what is consistent and correct use. The GSK definition is based on the definition provided by the International Conference on Harmonization (ICH) [ICH, M3 (R2) 2009].”

The investigator is responsible for ensuring that subjects understand how to properly use these methods of contraception.

This is an all inclusive list of those methods that meet the GSK definition of highly effective: having a failure rate of less than 1% per year when used consistently and, correctly and, when applicable, in accordance with the product label. For non-product methods (e.g. male sterility), the investigator determines what is consistent and correct use. The GSK definition is based on the definition provided by ICH [[ICH](#), M3 (R2) 2009].

The investigator is responsible for ensuring that subjects understand how to properly use these methods of contraception.

Females:

A female subject is eligible to participate if she is not pregnant (as confirmed by a negative urine human chorionic gonadotrophin (hCG) test), not lactating, and the following condition applies:

Non-reproductive potential defined as:

- Pre-menopausal females with one of the following:
 - Documented tubal ligation
 - Documented hysteroscopic tubal occlusion procedure with follow-up confirmation of bilateral tubal occlusion
 - Hysterectomy
 - Documented Bilateral Oophorectomy
- Postmenopausal defined as 12 months of spontaneous amenorrhea [in questionable cases a blood sample with simultaneous follicle stimulating hormone (FSH) and estradiol levels consistent with menopause (refer to laboratory reference ranges for confirmatory levels)]. Females on hormone replacement therapy (HRT) and whose menopausal status is in doubt will be required to use one of the highly effective contraception methods if they wish to continue their HRT during the study. Otherwise, they must discontinue HRT to allow confirmation of post-menopausal status prior to study enrolment.

The investigator is responsible for ensuring that subjects understand how to properly use these methods of contraception.

INFORMED CONSENT

9. Capable of giving signed informed consent as described in Section [7.2](#) which includes compliance with the requirements and restrictions listed in the consent form and in this protocol.

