5.2. Exclusion Criteria

A subject will not be eligible for inclusion in this study if any of the following criteria apply:

CONCURRENT CONDITIONS/MEDICAL HISTORY (INCLUDES LIVER FUNCTION AND QTc INTERVAL)

 1. ALT >1.5x Upper limit of normal (ULN). 2. Bilirubin >1.5xULN (isolated bilirubin >1.5xULN is acceptable if bilirubin is fractionated and direct bilirubin <35%). 3. Current or chronic history of liver disease, or known hepatic or biliary abnormalities (with the exception of Gilbert's syndrome or asymptomatic gallstones). 4. Prior history of altitude sickness. 5. Recently been scuba diving (within 1 week before screening). 6. QTc > 450 msec 
NOTES:
 
 • The QTc is the QT interval corrected for heart rate according to Bazett's formula (QTcB), Fridericia's formula (QTcF), and/or another method, machine-read or manually over-read. • The specific formula that will be used to determine eligibility and discontinuation for an individual subject should be determined prior to initiation of the study. In other words, several different formulae cannot be used to calculate the QTc for an individual subject and then the lowest QTc value used to include or discontinue the subject from the trial. • For purposes of data analysis, QTcB, QTcF, another QT correction formula, or a composite of available values of QTc will be used as specified in the Reporting and Analysis Plan (RAP).

CONCOMITANT MEDICATIONS

 7. Unable to refrain from prescription or non-prescription drugs, including agents active in the central nervous system, vitamins, herbal and dietary supplements (including St John's Wort) within 7 days (or 14 days if the drug is a potential enzyme inducer) or 5 half-lives (whichever is longer) prior to the first dose of study medication and throughout the study, unless in the opinion of the Investigator and/or GSK Medical Monitor (if needed) the medication will not interfere with the study procedures or compromise subject safety.

RELEVANT HABITS

8. History of regular alcohol consumption within 6 months of the study defined as:
 - An average weekly intake of >21 units for males or >14 units for females.
One unit is equivalent to 8 g of alcohol: a half-pint (~240 ml) of beer, 1 glass (125 ml) of wine or 1 (25 ml) measure of spirits

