Ventilatory parameters	X		X		X	X ¹			X		Measurements to be taken at the same time as the Echocardiograms. During the exercise challenge, an ECG integrated with the ventilatory assessment will be carried out.
Pulse Oximetry (O ₂ saturation)		←-----→									Will be continuously monitored for safety. Measurement should be recorded at time of each echocardiogram post-treatment and databased.
RAS Biomarkers	X	X ²	X ³	X ⁴		X ³		X ³	X ⁵	X ³	
Other Biomarkers	X	X ²	X ³	X ⁴		X ³		X ³	X ⁵	X ³	
PK sampling	X	X ²	X ³	X ⁴		X ³		X ³	X ⁵	X ³	

Procedure	Treatment Period 1 and 2 (Washout 3-14 days)										Notes
	Times relative to dosing				Hypoxia (Times relative to entry to Chamber)						
	Predose	0h	15 m	15-45m	0-60m	60m	60-70m	Immediately after exercise	30m rest on exit from chamber	After 30 mins rest	
AE/SAE review		←=====→									
Concomitant medication review	X										

1. To be taken at the end of exercise
2. Take at the end of the infusion
3. Taken immediately after echocardiogram
4. Immediately before entering the chamber
5. To be taken as soon as possible after leaving chamber

After written informed consent, screening assessments will be performed as outlined in the Time and Events Table (Section 7.1).

The following demographic parameters will be captured: year of birth, sex, race and ethnicity.

Medical/medication/family history will be assessed as related to the inclusion/exclusion criteria listed in Section 5.

Cardiovascular medical history/risk factors (as detailed in the CRF) will be assessed at screening.

Cardiorespiratory fitness during bicycle exercise and hypoxia tolerance will be assessed.

Procedures conducted as part of the subject's routine clinical management (e.g. blood count) and obtained prior to signing of informed consent may be utilized for Screening or baseline purposes provided the procedure meets the protocol-defined criteria and has been performed in the timeframe of the study.

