7.3.1. Exercise Challenge

Subjects will perform an exercise challenge at 70% of maximum VO₂ uptake on a cycle ergometer within the hypoxia chamber for 10 minutes as detailed in the SRM.

Subjects must complete a minimum of 5 minutes exercises at 70% of maximum_{max} VO₂ uptake.

Further details about the exercise challenge is detailed in the SRM.

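### Inclusion criterion 6 in Section 5.1 is worded as an exclusion: as written it requires a contraindication to bicycle exercise

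*Protocol*

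**What the plan says.** Section 5.1 opens with the rule that governs its list: "A subject will be eligible for inclusion in this study only if all of the following criteria apply". Nine numbered items follow. Item 5 is "Able to complete all study procedures". Item 6 is "Any contraindication (orthopaedic, cardiac etc.) to perform exercise on a bicycle ergometer". The same line, with the same number and in the same place, stands in the original protocol and in Amendment 01.

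Section 5.2 opens the other way: "A subject will not be eligible for inclusion in this study if any of the following criteria apply". That is the form of list that item 6 would fit as it is worded.

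Section 7.3.1 makes ergometer exercise in the hypoxia chamber a study procedure with a floor: "Subjects must complete a minimum of 5 minutes exercises at 70% of maximum" VO2 uptake.

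Section 5 adds that "Deviations from inclusion and exclusion criteria are not allowed because they can potentially jeopardize the scientific integrity of the study".

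**The concern.** An eligibility list is applied literally, item by item, and is audited that way. Item 6 gives the opposite of its evident purpose when it is applied that way, and Section 5 leaves no room for an informal workaround.

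The item also concerns safety. Subjects undergo an incremental exercise test at screening to find maximum oxygen uptake, and then exercise under simulated altitude in both treatment periods. The authors evidently wanted orthopaedic and cardiac contraindications checked, and the only criterion that names them points the wrong way.

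There is a record-keeping side too. Section 5.3 asks for eligibility-criteria details on screen failures. Someone turned away because of a contraindication would have to be recorded under a general criterion, since the one that names the reason is met rather than failed. The CRF is not shown; if it copies the protocol wording, its answers to item 6 would be inverted.

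**Working it through.** No arithmetic bears on this point. The check sets the relevant sections against each other.

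1. **Logic of the list.** Section 5.1 is conjunctive: a subject is eligible only if items 1 to 9 all hold. Item 6 holds when a contraindication is present. Eligibility as written therefore implies a contraindication to bicycle exercise.

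2. **Against criterion 5 and Section 7.3.1.** Criterion 5 requires the ability to complete all procedures. Section 7.3.1 makes at least 5 minutes of cycling at 70% of maximum VO2 one of them. Someone contraindicated for the ergometer cannot properly be said to satisfy criterion 5, so items 5 and 6 conflict within one list.

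3. **Against criterion 2.** Criterion 2 requires a subject judged healthy on a medical evaluation that includes cardiac monitoring. It admits unlisted abnormalities only if they are documented as unlikely to add risk and as not interfering with study procedures. A required contraindication to the main challenge procedure contradicts this.

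4. **Is the item stated correctly elsewhere?** Section 5.2 has 14 criteria in the original protocol. Amendment 01 adds two, on altitude sickness and recent scuba diving, giving 14 + 2 = 16. None of the 16 mentions exercise or a contraindication to it. The text after the Section 7.1 tables says "Cardiorespiratory fitness during bicycle exercise and hypoxia tolerance will be assessed", but attaches no eligibility threshold or contraindication check. That assessment is also itself exercise, so it cannot stand in for a check that should come before exercise.

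5. **Room for interpretation.** Section 5 rules out deviations from the criteria, and Section 7 rules out waivers except for immediate safety concerns. The text gives no route for setting item 6 aside.

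6. **Is it an extraction artefact?** The line is identical in two separately issued versions, so a PDF-reading error is an unlikely explanation.

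7. **Does it survive into Amendment 02?** The Amendment 02 change list for Section 5.1 shows edits to criterion 2 (spirometry added) and to criterion 8 (typographical), and none to item 6. In that list the sex criterion still carries the number 8, as before, which suggests that nothing ahead of it was moved out of the list. Neither fact rules out a silent rewording, because the change list is not complete. Appendix 2 of Amendment 01 carries a note on China for the acetaminophen adduct assay. Appendix 2 of Amendment 02 lacks the note, and the change-list entry for Section 12.2 covers only Footnote 4. Persistence is therefore likely but unverified.

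**The case against.** The strongest reply is that this is a clerical slip, a missing negative or a line in the wrong list. No site would apply it literally, because doing so would contradict criteria 2 and 5 and make the exercise challenge impossible. That is probably how it would play out in practice, and it limits the harm. It does not make the text right: this is an operative eligibility rule that gives the reverse result if followed, in a protocol that forbids departures.

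A reader might infer that the trial has no rule keeping subjects with a cardiac contraindication out of the exercise challenge. The documents do not support that. Criterion 2 requires a healthy subject. Criterion 3 requires a screening echocardiogram free of clinically significant abnormality. Criterion 5 requires ability to complete the procedures. Section 5.2 excludes QTc above 450 msec. Screening includes cardiovascular history and a supervised hypoxia and exercise test, and Section 5.4.1 provides for live saturation and telemetry monitoring with power to abort. What is absent is a correctly worded criterion naming exercise contraindications, not exercise safety as a whole.

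A reader might also infer that every sensibly enrolled subject becomes an eligibility violator and could be dropped from analysis. Section 9.3.1 does not lead there. The primary population is intent-to-treat. The sensitivity analyses are optional and follow a blind review for important deviations, and nothing suggests that such a review would count a healthy subject who can exercise as one.

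**Conclusion.** The point holds for Section 5.1 of the original protocol and of Amendment 01. Item 6 as written requires what it should screen out, contradicts criteria 2 and 5 and Section 7.3.1, and has no correctly worded counterpart in Section 5.2.

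Its size is one eligibility rule. No figure in the plan changes, and sample size, primary model and primary population are unaffected. It deserves correction because the rule bears on safety and is to be followed as written, not because it biases an estimate.

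The conclusion assumes that the item's purpose was to keep out people with a contraindication, which criteria 2 and 5 and the challenge itself make plain. It does not establish that the error stands in Amendment 02. A reader might take the silence of the change list as proof that it does, but Section 5.1 of that version is not shown and the list omits at least one other edit.

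**What to change.** First check Section 5.1 in the body of Amendment 02. If the line still stands, reconcile item 6 with the list heading, criterion 5 and Section 5.2. Either place it in Section 5.2, where its present wording fits, or keep it in Section 5.1 worded so that it fits a list in which every item must be true. Then check that the eligibility page of the CRF asks the question in the same direction, and correct any entries already made against the inverted wording.

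The cost is one line in the next amendment and one CRF check. Nothing in the design, sample size or analysis has to be reworked.

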5.2. Exclusion Criteria

A subject will not be eligible for inclusion in this study if any of the following criteria apply:

CONCURRENT CONDITIONS/MEDICAL HISTORY (INCLUDES LIVER FUNCTION AND QTc INTERVAL)

 1. ALT >1.5x Upper limit of normal (ULN). 2. Bilirubin >1.5xULN (isolated bilirubin >1.5xULN is acceptable if bilirubin is fractionated and direct bilirubin <35%). 3. Current or chronic history of liver disease, or known hepatic or biliary abnormalities (with the exception of Gilbert's syndrome or asymptomatic gallstones). 4. Prior history of altitude sickness. 5. Recently been scuba diving (within 1 week before screening). 6. QTc > 450 msec 
NOTES:
 
 • The QTc is the QT interval corrected for heart rate according to Bazett's formula (QTcB), Fridericia's formula (QTcF), and/or another method, machine-read or manually over-read. • The specific formula that will be used to determine eligibility and discontinuation for an individual subject should be determined prior to initiation of the study. In other words, several different formulae cannot be used to calculate the QTc for an individual subject and then the lowest QTc value used to include or discontinue the subject from the trial. • For purposes of data analysis, QTcB, QTcF, another QT correction formula, or a composite of available values of QTc will be used as specified in the Reporting and Analysis Plan (RAP).

CONCOMITANT MEDICATIONS

 7. Unable to refrain from prescription or non-prescription drugs, including agents active in the central nervous system, vitamins, herbal and dietary supplements (including St John's Wort) within 7 days (or 14 days if the drug is a potential enzyme inducer) or 5 half-lives (whichever is longer) prior to the first dose of study medication and throughout the study, unless in the opinion of the Investigator and/or GSK Medical Monitor (if needed) the medication will not interfere with the study procedures or compromise subject safety.

RELEVANT HABITS

8. History of regular alcohol consumption within 6 months of the study defined as:
 - An average weekly intake of >21 units for males or >14 units for females.
One unit is equivalent to 8 g of alcohol: a half-pint (~240 ml) of beer, 1 glass (125 ml) of wine or 1 (25 ml) measure of spirits
9. Urinary cotinine levels indicative of smoking or history or regular use of tobacco- or nicotine-containing products within 6 months prior to screening

CONTRAINdications

10. History of sensitivity to any of the study medications, or components thereof or a history of drug or other allergy that, in the opinion of the investigator or Medical Monitor, contraindicates their participation.

DIAGNOSTIC ASSESSMENTS AND OTHER CRITERIA

11. Presence of hepatitis B surface antigen (HBsAg), positive hepatitis C antibody test result at screening or within 3 months prior to first dose of study treatment. For potent immunosuppressive agents, subjects with presence of hepatitis B core antibody (HBcAb) should also be excluded.
12. A positive pre-study drug/alcohol screen.
13. A positive test for HIV antibody.
14. Where participation in the study would result in donation of blood or blood products in excess of 500 ml within 56 days.
15. The subject has participated in a clinical trial and has received an investigational product within the following time period prior to the first dosing day in the current study: 30 days, 5 half-lives or twice the duration of the biological effect of the investigational product (whichever is longer).
16. Exposure to more than four new chemical entities within 12 months prior to the first dosing day.

